7.2.3 Secondary endpoint analyses

The secondary endpoints for differences in PI at 10min and 1h under conditions 1 and 2 will be calculated from the same model as described for the primary analyses.

Additionally percent change from baseline in MED at 10min, 1h, and 24h will be calculated as ((MED_{on-drug}-MED_{baseline})/ MED_{baseline})*100 at each timepoint and the same model using described in the primary analysis will be used in the analyses of these endpoints.

c27983101-03 Clinical Trial Protocol Page 65 of 79

Proprietary confidential information © 2020 Boehringer Ingelheim International GmbH or one or more of its affiliated companies

7.2.5 Safety analyses

Adverse events will be coded using the Medical Dictionary for Drug Regulatory Activities (MedDRA). Standard BI summary tables and listings will be produced. All adverse events with an onset between start of treatment and end of the REP, a period of 7 days after the last dose of trial medication, will be assigned to the on-treatment period for evaluation.

The safety analysis will be done by 'randomised treatment'.

All treated subjects will be included in the safety analysis. In general, safety analyses will be descriptive in nature and will be based on BI standards. No hypothesis testing is planned.

Statistical analysis and reporting of adverse events will concentrate on treatment-emergent adverse events, i.e. all adverse events occurring between start of treatment and end of the REP. Adverse events that start before first drug intake and deteriorate under treatment will also be considered as 'treatment-emergent'.

Frequency, severity, and causal relationship of adverse events will be tabulated by system organ class and preferred term after coding according to the current version of the Medical Dictionary for Drug Regulatory Activities (MedDRA) at database lock.

c27983101-03 Clinical Trial Protocol Page 66 of 79

Proprietary confidential information © 2020 Boehringer Ingelheim International GmbH or one or more of its affiliated companies

Laboratory data will be analysed both quantitatively as well as qualitatively. The latter will be done via comparison of laboratory data to their reference ranges. Values outside the reference range as well as values defined as clinically relevant will be summarised. Treatment groups will be compared descriptively with regard to distribution parameters as well as with regard to frequency and percentage of subjects with abnormal values or clinically relevant abnormal values.

Vital signs, physical examinations, or other safety-relevant data observed at screening, baseline, during the course of the trial and at the end-of-trial evaluation will be assessed with regard to possible changes compared to findings before start of treatment.

7.2.6 Other Analyses

Details of other analyses, if needed, will be included in the TSAP.

7.2.7 Interim Analyses

No statistical interim analysis is planned. However, after completion of the 400mg dose group the independent Investigator and BI medical representatives will review blinded photosafety data of treatment A group to determine the acceptability of photosafety. After the team review of these data, it may be recommended, or in case of unfavourable results - to test the higher dose of 300mg BID for treatment A. In addition, a preliminary blinded PK analysis will be performed to estimate the PK exposure.

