Test product(s)	BI 730357 100 mg tablets
dose	400mg once daily
	300mg twice daily
mode of	p.o.

Boehringer Ingelheim

c27983101-03

BI Trial No.: 1407-0037

Clinical Trial Protocol

Page 4 of 79

01 Apr 2020

administration	
Comparator product(s)	Placebo matching BI 730357
dose	Not applicable
mode of administration	p.o.
Comparator product(s)	Ciprofloxacin
dose	500mg twice daily
mode of administration	p.o.
Duration of treatment	BI 730357 tablets or matching placebo over 8 days
	Ciprofloxacin over 5.5 days
Statistical methods	A mixed model for repeated measures on Phototoxicity index (PI) values will be utilized for the analysis of primary and secondary endpoints. The model will include treatment (BI 730357, Placebo, ciprofloxacin), time (10min, 1h, 24h, 48h, and 72h), and treatment-time interaction as fixed effects and subject as a random effect. Adjusted means and differences in PI and 90% CIs for the contrasts of interest (i.e. BI 703357 – placebo at 24h) will be calculated from the model.
	The analysis will be carried out separately for condition 1 and condition 2
	Descriptive statistics will be tabulated for all endpoints.

c27983101-03 Clinical Trial Protocol

Page 5 of 79

Proprietary confidential information © 2020 Boehringer Ingelheim International GmbH or one or more of its affiliated companies

FLOW CHART TREATMENT A 400 MG QD

Day	Planned time [h:min]	Approx. time [h:min]	Event and comment	Drug administration	Laboratory ¹	UVB/UVA irradiation	Photosensitivity assessment ⁴	Physical Exam	12-lead ECG ³	Vital signs ³	AE/Concomitant Medication
-28 to -3			Screening		X			X	X	X	X
-3						X^4	X^6				X
-2						X^7	X^5				X
-1			Admission		X	X^8	X ⁵	X	X	X	X
	-1:00	7:00	Predose/ Randomization				X ⁷				X
1	0:00	8:00		X							
	4:00	12:00									X
2	24:00	8:00		X							X
3	48:00	8:00		X							X
4	72:00	8:00		X							X
5	96:00	8:00		X							X
6	120:00	8:00		X							X
7	144:00	8:00		X							X
8	168:00	8:00		X	X						X
	169:00	9:00									
	170:00	10:00				X					
	170:10	10:10					X				
	171:00	11:00					X				
	172:00	12:00									
	174:00	14:00									
	180:00	20:00									
9	192:00	8:00									X
	194:00	10:00					X				
10	216:00	8:00									X
	218:00	10:00					X				
11	240:00	8:00						X	X	X	X
	242:00	10:00	Discharge				X				
15			EOT ²		X			X	X	X	X

c27983101-03 Clinical Trial Protocol

Page 6 of 79

Proprietary confidential information © 2020 Boehringer Ingelheim International GmbH or one or more of its affiliated companies

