4.1.2 Selection of doses in the trial and dose modifications

The dose of 400 mg BI 730357 QD or 300 mg BID for this trial are selected on the basis of the PK and safety data obtained in the SRD and MRD trials 1407.0001 and 1407-0002, preliminary PK and safety data obtained in patients with plaque psoriasis in the ongoing 1407.30 study, combined with the preclinical data (see section 1.1), are intended to cover the highest therapeutic dose range (including safety margin) chosen for the future clinical development of BI 730357 in diverse indications.

In the SRD trial, single dose levels up to 800 mg and in the MRD trial, multiple dose levels up to 400 mg were well tolerated in healthy volunteers, and doses up to 200mg were well tolerated in plaque psoriasis patients.

Blinded photosafety data will be evaluated by the independent Investigator and BI medical team after completion of the 400 mg BI 730357 or placebo QD treatment.

If no photo-safety concerns have been observed in the Treatment A group,300 mg BI 730357 or placebo BID will be conducted.

The Ciprofloxacin dose selected in this trial reflects the standard clinical dose with acceptable safety profile. Ciprofloxacin was chosen as the positive control based on its property as mild photosensitizer (R 19-2246, R 19-3127).

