4. PLANNED ANALYSES

4.1. INTERIM ANALYSIS

There are no formal statistical interim analyses planned for this study. However, after completion of the 400mg dose group, the independent Investigator and BI medical representatives will review blinded photosafety data of treatment A group to determine the acceptability of photosafety. After the team review of these data, it may be recommended to terminate the trial based on favourable results of 400mg, or in case of unfavourable results - to test the lower dose in of 200mg for treatment A. However, primary analysis of ongoing PoC trial have shown higher exposures in Psoriasis patients than those of healthy volunteers; therefore, in order to investigate possible phototoxic effects in exposures which approximate those of patients treated with 200 mg BID, healthy volunteers should be treated with 300 mg BID. under fed conditions in this trial.

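### The decision rule after the 400 mg QD cohort is contradictory: Protocol 4.1.2, Protocol 7.2.7 and SAP 4.1 attach different consequences to the same blinded photosafety review

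*Protocol*

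**What the plan says.** Protocol 7.2.7 plans no statistical interim analysis, but once the 400 mg group is complete the independent investigator and the sponsor's medical representatives "will review blinded photosafety data of treatment A group to determine the acceptability of photosafety". On what follows, it says: "it may be recommended, or in case of unfavourable results - to test the higher dose of 300mg BID for treatment A".

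Protocol 4.1.2, the dose-selection section, describes the same review and says: "If no photo-safety concerns have been observed in the Treatment A group,300 mg BI 730357 or placebo BID will be conducted". It does not say what happens if there are concerns.

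SAP 4.1 also describes the same review. For favourable results, "it may be recommended to terminate the trial based on favourable results of 400mg". Otherwise, "in case of unfavourable results - to test the lower dose in of 200mg for treatment A". The paragraph then turns with a however: exposures in psoriasis patients were higher than in healthy volunteers, and for that reason "healthy volunteers should be treated with 300 mg BID". No photosafety condition is attached to that last statement.

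Elsewhere the second cohort is planned without any condition: Protocol 4.1.3 and 7.4 describe its enrolment and randomisation, and Protocol 7.5 counts its 36 subjects in the total of 84.

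**The concern.** This review is the only decision step between the two dose cohorts that the visible text specifies. The participants are healthy volunteers with no therapeutic benefit (Protocol 1.4.1), and the compound has phototoxicity potential in non-clinical work (Protocol 1.2 and 1.3). Read literally, Protocol 7.2.7 would move volunteers to a higher daily dose because the lower one gave an unfavourable photosafety result. Protocol 4.1.2 makes the absence of concerns the condition for the same step.

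The protocol's own figures show why the direction of the rule matters. Protocol 1.4.2 gives a steady-state AUC of 35,500 nmol·h/L for 400 mg QD. The rat dose without cutaneous phototoxic reactions gave 35,200 nM·h, a ratio of 35,500 / 35,200 = 1.01. The peak-concentration ratio is lower: 2,210 / 4,520 = 0.49.

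There is an inferential side too. The 300 mg BID comparison with placebo (Protocol 7.1, SAP 15.3.2) can be made only if that cohort is run. A reader cannot tell from the plan under which outcome of the first cohort that happens.

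**Working it through.** The check is a comparison of trigger and action in each section. No power, alpha or sample-size figure is involved.

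**Are all three sections current?** Protocol 4.1.2 and 7.2.7 stand in the body of Version 3.0. SAP 4.1 stands in the body of Version 2.0, and the SAP Introduction says that version is based on Protocol Version 3.0. The visible text of SAP 3.3, which lists changes from the protocol, does not mention this rule. Nothing here depends on the amendment log.

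**Side by side:**

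| Outcome of the blinded review | Protocol 4.1.2 | Protocol 7.2.7 | SAP 4.1 |
|---|---|---|---|
| Favourable, or no concerns | Run 300 mg BID | No action visible; the sentence breaks off | May terminate the trial; then 300 mg BID after the however |
| Unfavourable, or concerns | Condition for 300 mg BID not met; no action stated | Test 300 mg BID | Test 200 mg; then 300 mg BID after the however |

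The three columns agree in neither row. In the unfavourable row, one result leads to no stated action, to a higher dose, or to a lower dose. SAP 4.1 also conflicts with itself, because its closing statement on 300 mg BID fits neither of the two options before it.

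**Does any criterion settle the conflict?** No visible passage defines an unfavourable result or a photosafety concern numerically, so no threshold shows which branch applies.

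**Is 300 mg BID the higher dose?** Yes, as Table 4.1.4:2 of the protocol confirms:

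- First cohort: 400 mg × 1 = 400 mg per day.
- Second cohort: 300 mg × 2 = 600 mg per day.
- Ratio: 600 / 400 = 1.5.

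**Who is affected?** The second cohort has 36 subjects, 27 on active drug and 9 on placebo (Protocol 3.2).

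**The case against.** The strongest reply is that this is an editing slip and not an intended rule. The sentence in Protocol 7.2.7 is grammatically incomplete and closely parallels the one in SAP 4.1, as if 300 mg BID had replaced an older option and words had dropped out. Protocol 4.1.2 states a clear condition in the section devoted to dose selection. The SAP does not govern dosing, and its closing statement can be read as setting the older options aside. Protocol 3.3.4.1 and 3.3.4.3 let the sponsor stop treatment or the trial on safety grounds. Protocol 1.2 expects exposures at 300 mg BID to stay within the 13-week NOAEL thresholds. If the cohort runs, its analysis is fully specified.

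Much of this is fair. An incomplete edit is the likeliest explanation, although that is an inference. The blank for favourable results in Protocol 7.2.7 may be a redaction or a loss in text extraction, so no weight is placed on it. The SAP does not say that photosafety results are to be ignored; it simply attaches no such condition to 300 mg BID.

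The contradiction survives all of this. The clause tying unfavourable results to the higher dose is intact and conflicts with Protocol 4.1.2. No visible text gives one section precedence over another. General stopping powers are not a rule for moving between cohorts. An expected exposure below a general-toxicity threshold does not say what follows an unfavourable photosafety finding.

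**Conclusion.** The concern holds and should be corrected before the rule is relied on. For one and the same review, Protocol 4.1.2 makes 300 mg BID conditional on the absence of concerns, and Protocol 7.2.7 links it to unfavourable results. SAP 4.1 gives a stop-or-200-mg choice and then 300 mg BID with no photosafety condition. The size is a whole cohort: 36 subjects, 27 on active drug, at 1.5 times the first cohort's daily dose. No estimate, error rate or sample size changes.

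The conclusion rests on reading the sections as they stand and does not depend on whatever may be missing from the broken sentence in Protocol 7.2.7. The documents do not say whether the decision had already been taken when SAP Version 2.0 was finalised. This assessment takes no position on which dose or action is right.

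**What to change.** Reconcile Protocol 4.1.2, Protocol 7.2.7 and SAP 4.1 into a single rule worded identically in all three places. State exactly one action for each outcome of the blinded review and delete the alternatives that no longer apply. Bring the sections that plan the second cohort unconditionally (Protocol 4.1.3, 7.4 and 7.5) into line by referring to that rule. The choice of action for each outcome belongs to the sponsor's medical team and the investigator. If the review has already taken place, the trial report should say which rule was applied and what the review concluded.

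The cost is wording in two protocol sections and one SAP section, plus the cross-references. Data collection, sample size and the planned models are unaffected.

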7.3 HANDLING OF MISSING DATA

No imputation is planned for missing MED, PI, or assessments of skin reaction data.

7.4 RANDOMISATION

The first set of subjects will be first randomised to the Treatment A (BI 400 mg QD/placebo) or Treatment B group in a 3:1 ratio. The random list will be provided by BI to the dedicated study staff.

Subjects allocated to the treatment group A will be randomised in a 3:1 ratio in a double blind manner, which reflects the ratio of subjects receiving active drug to placebo.

Subjects allocated to treatment B group will receive ciprofloxacin.

In order to investigate a second BI730357 dose of 300 mg BID, a second set of subjects be randomised in a 3:1 ratio in the same double blind manner described for Treatment A above, which reflects the ratio of subjects receiving active drug to placebo.

c27983101-03 Clinical Trial Protocol Page 67 of 79

Proprietary confidential information © 2020 Boehringer Ingelheim International GmbH or one or more of its affiliated companies

BI will arrange for the randomisation as well as packaging and labelling of trial medication for treatment A. The randomisation list will be generated using a validated system, which involves a pseudo-random number generator so that the resulting treatment will be both reproducible and non-predictable. The block size will be documented in the Clinical Trial Report. Access to the codes will be controlled and documented.

More details can be found in section 4.1.5.

7.5 DETERMINATION OF SAMPLE SIZE

It is planned to include initially a total of 84 healthy male and female subjects (36 subjects for Treatment A 400 mg QD, 36 subject for Treatment A 300 mg BID; 12 subjects for Treatment B) in this trial.

The planned numbers of subjects should be sufficient for the exploratory evaluation of photosafety of each of the BI 730357 dose groups. Based on a similarly designed study for evaluation of pradigastat the observed mean (standard deviation) over all PI measurements for 9 patients who received placebo and 12 subjects who received ciprofloxacin was 1.08 (0.12) and 1.61 (0.55), respectively (R19-3037).

Assuming a common standard deviation of 0.15 and an expected difference in mean PI of 0 between BI 730357 and placebo, each of the two group 0.05 one-sided t-tests will have 99% power to reject the null hypothesis that BI 730357 and placebo are not equivalent (the difference in means, μ_{BI} - μ_{pbo} , is \geq 0.4 and μ_{BI} - $\mu_{pbo} \leq$ -0.4) in favor of the alternative hypothesis that the means of the two groups are equivalent (nQuery Advisor, version 7).

Additionally, for the planned comparison of mean PIs for BI 730357 and ciprofloicin, a two group Satterthwaite t-test with a 0.05 two-sided significance level will have 87% power to detect a difference in means of 0.6 (the difference between μ_{cipro} of 1.60 and a μ_{BI} of 1.0) assuming standard deviation of ciprofloxacin is 0.600 and standard deviation for BI 730357 is 0.15 when the sample sizes in the two groups are 12 and 27, respectively (nQuery Advisor, version 7). Using the same assumptions and calculation for 12 ciprofloxacin and 9 placebo instead of 27 BI 370357 subjects the power is 86%. Based on the similar study of pradigastat, the drop-out rate will be minimal. Further details will be discussed in the TSAP.

c27983101-03 Clinical Trial Protocol Page 68 of 79

Proprietary confidential information © 2020 Boehringer Ingelheim International GmbH or one or more of its affiliated companies

8. INFORMED CONSENT, TRIAL RECORDS, DATA PROTECTION, PUBLICATION POLICY, AND ADMINISTRATIVE STRUCTURE

The trial will be carried out in compliance with the protocol, the ethical principles laid down in the Declaration of Helsinki, in accordance with the ICH Harmonized Guideline for Good Clinical Practice (GCP), relevant BI Standard Operating Procedures (SOPs), the EU directive 2001/20/EC / EU regulation 536/2014 and other relevant regulations. Investigators and site staff must adhere to these principles. Deviation from the protocol, the principles of ICH GCP or applicable regulations as will be treated as "protocol deviation".

Standard medical care (prophylactic, diagnostic and therapeutic procedures) remains the responsibility of the treating physician of the patient.

The investigator will inform the sponsor immediately of any urgent safety measures taken to protect the trial participants against any immediate hazard, as well as of any serious breaches of the protocol or of ICH GCP.

The Boehringer Ingelheim transparency and publication policy can be found on the following web page: trials.boehringer-ingelheim.com. The rights of the investigator and of the sponsor with regard to publication of the results of this trial are described in the investigator contract. As a rule, no trial results should be published prior to finalisation of the Clinical Trial Report.

8.1 TRIAL APPROVAL, PATIENT INFORMATION, INFORMED CONSENT

This trial will be initiated only after all required legal documentation has been reviewed and approved by the respective Institutional Review Board (IRB / Independent Ethics Committee (IEC and competent authority (CA) according to national and international regulations. The same applies for the implementation of changes introduced by amendments.

Prior to patient participation in the trial, written informed consent must be obtained from each patient (or the patient's legally accepted representative) according to ICH-GCP and to the regulatory and legal requirements of the participating country. Each signature must be personally dated by each signatory and the informed consent and any additional patient-information form retained by the investigator as part of the trial records. A signed copy of the informed consent and any additional patient information must be given to each patient or the patient's legally accepted representative."

c27983101-03 Clinical Trial Protocol Page 69 of 79

Proprietary confidential information © 2020 Boehringer Ingelheim International GmbH or one or more of its affiliated companies

8.2 DATA QUALITY ASSURANCE

A risk-based approach is used for trial quality management. It is initiated by the assessment of critical data and processes for trial subject protection and reliability of the results as well as identification and assessment of associated risks. An Integrated Quality and Risk Management Plan documents the rationale and strategies for risk management during trial conduct including monitoring approaches, vendor management and other processes focusing on areas of greatest risk.

Continuous risk review and assessment may lead to adjustments in trial conduct, trial design or monitoring approaches.

A quality assurance audit/inspection of this trial may be conducted by the sponsor, sponsor's designees, or by IRB / IEC or by regulatory authorities. The quality assurance auditor will have access to all medical records, the investigator's trial-related files and correspondence, and the informed consent documentation of this clinical trial.

8.3 RECORDS

CRFs for individual subjects will be provided by the sponsor. See section 4.1.5.2 for rules about emergency code breaks. For drug accountability, refer to section 4.1.8.

8.3.1 Source documents

In accordance with regulatory requirements, the investigator should prepare and maintain adequate and accurate source documents and trial records that include all observations and other data pertinent to the investigation on each trial patient. Source data as well as reported data should follow the "ALCOA principles" and be attributable, legible, contemporaneous, original and accurate. Changes to the data should be traceable (audit trail).

Data reported on the CRF must be consistent with the source data or the discrepancies must be explained.

Before providing any copy of subjects' source documents to the sponsor, the investigator must ensure that all patient identifiers (e.g. patient's name, initials, address, phone number, social security number) have properly been removed or redacted from any copy of the subjects' source documents.

If the subject is not compliant with the protocol, any corrective action e.g. re-training must be documented in the subject file.

For the CRF, data must be derived from source documents, for example:

- Subject identification: gender, year of birth (in accordance with local laws and regulations)
- Subject participation in the trial (substance, trial number, patient number, date patient was informed)
- Dates of Subject's visits, including dispensing of trial medication
- Medical history (including trial indication and concomitant diseases, if applicable)

c27983101-03 Clinical Trial Protocol Page 70 of 79

Proprietary confidential information © 2020 Boehringer Ingelheim International GmbH or one or more of its affiliated companies

- Medication history
- Adverse events and outcome events (onset date (mandatory), and end date (if available))
- Serious adverse events (onset date (mandatory), and end date (if available))
- Concomitant therapy (start date, changes)
- Originals or copies of laboratory results and other imaging or testing results, with proper documented medical evaluation (in validated electronic format, if available)
- Completion of Subject's participation in the trial" (end date; in case of premature discontinuation document the reason for it).
- Prior to allocation of a Subject to a treatment into a clinical trial, there must be documented evidence in the source data (e.g. medical records) that the trial participant meets all inclusion criteria and does not meet any exclusion criteria. The absence of records (either medical records, verbal documented feedback of the Subject or testing conducted specific for a protocol) to support inclusion/exclusion criteria does not make the Subject eligible for the clinical trial.

